
 • All female participants who accepted bone densitometry measurement • Women aged 40-55 years with an intact uterus • BMI of < 34.0 kg/m², and > 7 moderate-to-severe hot flushes daily • Women will be considered to be postmenopausal if they had had either > 12 months of spontaneous amenorrhea or > 6 months of spontaneous amenorrhea with serum follicle-stimulating hormone levels of > 40 mIU/mL
Exclusion criteria

 • Diabetes • Secondary obesity • Gastrointestinal diseases • Use of dietary supplements, including calcium, in the three months before enrollment • Pharmacotherapy of lipid disorders or hypertension in the three months before enrollment • Clinically significant acute inflammatory process • Antibiotics intake within the month before enrollment • Participation in a body mass management study • The use of drugs known to modify body mass or food intake • Abuse of alcohol, nicotine, or drugs • Hormone replacement therapy • Vegetarian diet • Use of probiotic enriched or prebiotic enriched products in the three weeks before enrollment • Consumption of products with high dietary fiber content, or consumption of more than 400 g of fermented food a day • Diagnosed osteoporosis

Figure 2. Inclusion and Exclusion criteria

Interventions or exposures

[figure not shown]

Figure 3. Diagram of the intervention period

The intervention period during this study can be seen in figure 3. The diet intervention in this experiment will be performed for 12 weeks, as Ahn et al. (2019) described. Two groups will be designated in this study. Group 1 is the placebo group that will receive a capsule that consists of the excipient. The excipient will be composed of maize starch and maltodextrins (Skrypnik et al., 2019). Group 2 is the probiotic group that will receive a diet capsule consisting of *Lactobacillus acidophilus* with a dose of 1×10^9 CFU with the excipient described by Hosseini et al. (2019). In addition, it is essential to deliver self-administration of probiotic agents orally in the morning with fasting conditions to evaluate probiotic effectiveness. Subsequently, patients will be asked to keep the diet in refrigerated condition (2-7 °C).

Primary endpoints

This study will consider the change from baseline in the frequency and severity of hot flushes as primary endpoints.

Secondary endpoints

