Meanwhile, the health-related quality of life, sleep, satisfaction with treatment, and cumulative amenorrhea and breast pain will be considered as secondary endpoints.

Sample size calculation

To calculate sample size, this study refers to the Soleimani et al. (2017) study. Using a formula suggested for clinical trials, having 25 participants in each group will be considered adequate

while considering a type I error (a) of 0.05 and type II error (b) of 0.20 (power $1 - \beta = 80\%$), with 1.61 as the SD and 1.30 as the mean distinction of CTX for markers of bone resorption and BSAP for marker of bone formation as the key variable. By assuming five dropouts in each group, the final sample size will be 30 participants in each group.

Methods assignment of interventions

Randomization will be performed using a computerized random number generator, which generated the random sequence based on simple randomization. All subjects will be identified by a trial identification number and assigned a treatment code. The researchers and participants will be blinded to the treatment code until the end of the study when data will be collected and evaluated. The groups will be decided after the completion of the data analysis.

Variable assessment

All information is containing 3 days dietary records, body composition measurement, and fasting blood samples will be collected at the beginning and end of the study. DIETA 6.0 and 5D computer program by Instytut Żywości i Żywienia, Poland will be used for analyzing 3 days averages of macronutrients and micronutrient intakes. A validated questionnaire obtains personal and demographic information. Anthropometric measurements will be measured using body composition analysis.

Biomarkers of bone turnover and hormones

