This study will analyze the biomarkers of bone turnover and hormones as described by Villareal et al. (2016). Briefly, venous blood samples will be obtained after fasting overnight and analyzed in the laboratory. Enzyme-linked immunosorbent assay (ELISA) will be used to measure C-terminal telopeptide of type I collagen (CTX) and tartrate-resistant acid phosphatase isoform-5b (TRAP5b) as markers of bone resorption and bone-specific alkaline phosphatase (BSAP) as a marker of bone formation. Radioimmunoassay will be used to measure N-terminal propeptide of type I procollagen (PINP) as an additional marker of bone formation. ELISA is also used to measure high-molecular-weight adiponectin and insulin-like growth factor-1. Chemiluminescent immunoassays will be used to measure parathyroid hormone (PTH) and cortisol.

Hair sample

A hair strand of 1 cm of length is collected from the occipital region. The sample will be taken by a member of the study team shortly after the hair had been washed with a shampoo not containing functional components. Each woman is instructed on how to wash her hair. Moreover, it will be clearly explained to patients that reliable results could be obtained only by complying with this procedure. Hair spray or hair dye is forbidden during the study (Skrypnik et al., 2019).

Calcium analysis

The calcium contents of the hair and serum will be determined after digestion in 65% (w/w) spectra pure HNO₃ using a Microwave Digestion System. Upon digestion and dilution with deionized water, the concentrations in the mineral solutions are measured using flame atomic absorption spectrometry (Skrypnik et al., 2019).

Bone densitometry analysis

This analysis will be conducted in the accredited laboratory in Poznan, Poland. Subsequently, the subjects are asked to undergo bone mineral densitometry using a DEXA scan. The scan will be performed on a Hologic DXA scan machine.

Products used in the research

1. A capsule consists of Maize starch and maltodextrins for the Placebo Group.
2. A capsule contains *Lactobacillus acidophilus* with a dose of 1×10^9 CFU for the Probiotic Group.

Ascertainment Feasibility

The study will be conducted in the Department of Obesity and Metabolic Disorders Treatment and Clinical Dietetics, Karol Marcinkowski University of Medical Sciences (PUMS), Poznan, Poland. This place receives patients who meet the inclusion criteria described above.

Techniques and actual available equipment

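### Cumulative amenorrhea is a poor secondary efficacy endpoint because women must already be amenorrheic to enter, while no listed endpoint measures the calcium and bone aim

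*Protocol*

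**What the plan says.** Protocol, Secondary endpoints: after quality of life, sleep and treatment satisfaction, the list ends "cumulative amenorrhea and breast pain will be considered as secondary endpoints". The protocol does not define cumulative amenorrhea, say how bleeding is recorded, or give an expected rate.

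Protocol, Eligibility criteria, Figure 2, offers two routes to postmenopausal status. The first reads "Women will be considered to be postmenopausal if they had had either > 12 months of spontaneous amenorrhea". The second reads "> 6 months of spontaneous amenorrhea with serum follicle-stimulating hormone levels of > 40 mIU/mL". The same figure admits "Women aged 40-55 years with an intact uterus" and lists "Hormone replacement therapy" among the exclusions.

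Protocol, Products used in the research, describes the two arms: "A capsule consists of Maize starch and maltodextrins for the Placebo Group", and "A capsule contains *Lactobacillus acidophilus* with a dose of 1×10^9 CFU for the Probiotic Group". Under Interventions or exposures, both are taken for 12 weeks.

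Protocol, Aim of study, sets the aim as the effect on calcium status and bone densitometry. The assessment sections describe CTX, TRAP5b, BSAP, PINP, PTH, hair and serum calcium, and DXA. None of these appears under Primary endpoints or Secondary endpoints. CTX and BSAP appear only as the key variable of the sample size calculation.

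**The concern.** The entry rule selects women on the very state that the endpoint measures. A woman who enters amenorrheic cannot improve on it; the only possible movement is new bleeding. An efficacy endpoint that can move only in the unfavourable direction, and that few women are likely to move on, gives almost no information about the probiotic. The protocol also gives no reason why the probiotic should alter bleeding.

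Two things are at stake. A finding of no difference in amenorrhea would be nearly certain whatever the product does, and could be misread as evidence. And the measurements that answer the study question have no endpoint status in this document, so which of them to emphasise could be decided after the data are seen.

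**Working it through.** **The plan's own figure.** The only calculation in the protocol concerns bone markers: SD 1.61, difference 1.30, type I error 0.05, power 80%. Taken as two-sided:

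n = 2 × (1.960 + 0.842)² × 1.61² / 1.30² = 2 × 7.849 × 2.592 / 1.690 = 24.1, so 25 per group.

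Adding five dropouts gives 30. The stated numbers reproduce, but they say nothing about amenorrhea.

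**Inputs for amenorrhea.**
- Group size: 25 evaluable or 30 randomised per group (Protocol, Sample size calculation).
- Bleeding rate over 12 weeks: not given. Assumed range 0-10% in one group and 0% in the other.
- Scale and test: not given. Assumed to be a yes/no outcome per woman, compared by a two-sided Fisher exact test at 0.05.

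**Step 1: the smallest significant split.** With no bleeding in one group and k women bleeding in the other, p = 2 × C(n, k) / C(2n, k).

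| Split | n = 25 | n = 30 |
|---|---|---|
| 5 vs 0 | 2 × 53,130 / 2,118,760 = 0.0502 | 2 × 142,506 / 5,461,512 = 0.0522 |
| 6 vs 0 | 2 × 177,100 / 15,890,700 = 0.0223 | 2 × 593,775 / 50,063,860 = 0.0237 |

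At either size, at least 6 against 0 is needed.

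**Step 2: the chance of reaching it.** This is P(X ≥ 6) for X binomial (n, rate).

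| Assumed bleeding rate in one group, none in the other | n = 25 | n = 30 | n per group for 80% power |
|---|---|---|---|
| 2% | about 0% | about 0% | 388 |
| 5% | 0.12% | 0.33% | 152 |
| 10% | 3.3% | 7.3% | 74 |

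The last column uses the normal approximation for two proportions with a pooled variance under the null. For 90% against 100% amenorrheic: (1.960 × √(2 × 0.95 × 0.05) + 0.842 × √(0.90 × 0.10))² / 0.10² = 73.4, so 74.

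**Step 3: sensitivity.** If some women bleed in both groups, the picture is similar. Amenorrhea rates of 90% against 98% give power of 2.3% (n = 25) and 4.3% (n = 30); 95% against 99% gives 0.1% and 0.2%. Only a much larger gap changes this: 80% against 100% would give 38% and 57%. That would require one woman in five to resume bleeding within 12 weeks in one arm only, and nothing in the protocol suggests this.

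**Step 4: listed endpoints against the aim.**

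| | Calcium or bone measure? |
|---|---|
| Primary: frequency and severity of hot flushes | No |
| Secondary: quality of life, sleep, satisfaction, amenorrhea, breast pain | No |
| Collected without endpoint status: CTX, TRAP5b, BSAP, PINP, PTH, hair and serum calcium, BMD | Yes, except that PTH is a related hormone |

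**The case against.** **The endpoint is not literally fixed.** A reader might infer that the entry rule sets amenorrhea at 100% and that the endpoint can show nothing. The documents do not support that. The rule describes the past, not the next 12 weeks, and it admits women of 40 to 55 with a uterus after little more than six months without bleeding. Some may bleed, and recording it could have descriptive or safety value. This objection stands, and it limits the claim to a probable ceiling with very little chance of showing a treatment difference.

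**Breast pain.** A reader might want to delete it on the same ground. No entry criterion concerns breast pain and the calculation above does not cover it, so the ceiling argument gives no reason to remove it.

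**Multiplicity.** It might also be inferred that amenorrhea uses up part of a secondary error budget. The protocol defines no family, hierarchy or alpha allocation. That is commonly left to a statistical analysis plan, which is not at hand, so no such cost is claimed.

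**Low power for a secondary endpoint is ordinary.** This is true, and the scale and test used here are assumptions because the endpoint is undefined. The complaint, however, is that selection at entry has removed most of the room for variation. Another test or scale would not restore it.

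**Bone measures could be added without deleting anything.** This is also true: listing amenorrhea does not cause their absence. The two changes are proposed together because they amend the same sentence. The protocol does name turnover, hair calcium and DXA as before-and-after parameters in its Short Description, but it does not make them endpoints.

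**Conclusion.** The point holds in a limited form. Cumulative amenorrhea will probably be near ceiling in both groups and is unlikely to show a treatment difference. With an assumed bleeding rate of up to 10% in one group and none in the other, the chance of significance is at most about 3% (25 per group) or 7% (30 per group). This rests on the assumed rate, a yes/no outcome and a Fisher test, none of which the protocol states. The qualitative conclusion rests on the entry rule, the hormone exclusion, the described capsules and the 12-week period, all of which it does state.

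The second part needs no assumption: no listed primary or secondary endpoint measures calcium status or bone densitometry.

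The primary analysis and the sample size are not affected. The mismatch between the hot-flush primary endpoint and the bone aim is a separate matter. Settling it would not remove the amenorrhea endpoint.

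**What to change.** Amend the Secondary endpoints paragraph of the protocol:

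1. Remove cumulative amenorrhea from the secondary efficacy endpoints. Record any vaginal bleeding during the 12 weeks and report it descriptively by group as a safety observation. Patients are already asked to tell the researchers of medical changes; the protocol should say that bleeding is among them and how it is noted.
2. Name as secondary endpoints the changes from baseline to week 12 in hair calcium, serum calcium, BMD by DXA, CTX, TRAP5b, BSAP, PINP and PTH, except any of these that is made primary.
3. Breast pain may stay as a descriptive measure.

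**Cost.** A few sentences are reworded. All the named measurements are already planned, so no extra visit, sample or participant is needed. The downside is one symptom endpoint fewer and a longer secondary list, which should be read as supportive.

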Can *Lactobacillus acidophilus* decrease the risk of postmenopausal osteoporosis in women?

Short Description

Background

The current recommendations for treating bone diseases are estrogen therapy and pharmacological agents. However, those treatments increase the risk of cancers and are not prescribed for long-term use. *Lactobacillus acidophilus* in ovariectomized mice could inhibit osteoclastogenic cells and promote anti-osteoclastogenic cells.

Aim of study

This study aims to evaluate the effect of *L. acidophilus* supplementation on calcium status and bone densitometry in postmenopausal women in a randomized, double-blind placebo-controlled study.

Study design

This study has three steps; namely, **1st step** is to prepare the diet supplementation of probiotics (*L. acidophilus* 1×10^9 CFU). **2nd step** is to perform the randomized, double-blind placebo-controlled clinical trial. **3rd step** is to analyze the effects of *L. acidophilus* in postmenopausal women.

Methods & Analysis

60 women of postmenopausal osteoporosis will be recruited by following inclusion and exclusion criteria. Participants will be randomized and divided into two groups to take a capsule containing probiotics and a placebo for 12 weeks. Before and after the intervention, several parameters will be conducted, such as the bone turnover and hormones parameter in blood using ELISA, the calcium mineralization in hair sample using AAS, the bone densitometry analysis in bone using DXA.

Research Design

Study settings

This study will be conducted within two (2) years for research activity and one (1) year for the publication period. There are three steps within this study; namely, **1st step** is to prepare the sample of *L. acidophilus* as diet supplementation. Probiotic capsules will contain *L. acidophilus* 1×10^9 CFU. **2nd step** is to perform the randomized, double-blind placebo-controlled clinical trial of *L. acidophilus* supplementation for twelve weeks (Figure 1). **3rd step** is to analyze the effects of *L. acidophilus* in postmenopausal women.

[figure not shown]

Figure 1. Flow diagram of patient recruitment

Eligibility criteria (inclusion, exclusion criteria)

The inclusion and exclusion criteria are provided in figure 2. Informed consent should be obtained from all patients, and the patients will be asked to notify the researchers if medical changes occurred during the intervention.

Inclusion criteria

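### Simple randomization of 60 women does not guarantee the stated 30 per group; permuted blocks that close at 60 would, at little cost.

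*Protocol*

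**What the plan says.** The Methods & Analysis paragraph of the Protocol fixes the total, "60 women of postmenopausal osteoporosis will be recruited", and the number of arms, "Participants will be randomized and divided into two groups".

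Under Sample size calculation, "having 25 participants in each group will be considered adequate". Five assumed dropouts are then added to each group, so that "the final sample size will be 30 participants in each group".

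The next section, Methods assignment of interventions, describes a computerized random number generator "which generated the random sequence based on simple randomization". No section mentions blocks, strata or any limit on arm size. The same section gives the blinding: "The researchers and participants will be blinded to the treatment code until the end of the study".

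**The concern.** Simple randomization assigns each woman independently of the others, so the arm sizes are random. The protocol gives a definite number per group and, in the next section, an allocation method that seldom produces it. The risk is not bias. Unequal arms estimate a difference between means less precisely than equal arms of the same total, and an unlucky list could start one arm below the 25 that the sizing treats as adequate, before any dropout. The question is how often this happens and how much it costs.

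**Working it through.** **Inputs.** All come from the Protocol: total 60 in two groups; 25 completers and 30 randomized per group; alpha 0.05; power 80%; SD 1.61; mean difference 1.30; five dropouts per group. Two points are assumed. The ratio is taken as 1:1, as 30 per group implies. Alpha is taken as two-sided, because the protocol gives only "type I error (a) of 0.05" and the two-sided reading reproduces its number (one-sided would give 19 per group).

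**1. The protocol's own figure.** n per group = 2 × [SD × (z₀.₉₇₅ + z₀.₈₀) / difference]² = 2 × [1.61 × (1.960 + 0.842) / 1.30]² = 24.08, rounded up to 25. Then 25 + 5 = 30 per group and 2 × 30 = 60. The sample size reproduces.

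**2. Arm sizes under simple randomization.** Let X be the size of one arm, X ~ Binomial(60, 0.5).

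- Exactly 30:30: P(X = 30) = 0.1026, or 10.3%.
- Split of 25:35 or worse: 2 × P(X ≤ 25) = 0.245, or 24.5%.
- One arm below 25: 2 × P(X ≤ 24) = 0.155, or 15.5%.
- Central 95% range for one arm: 22 to 38.
- Mean absolute difference between arms: 60 × P(X = 30) = 60 × 0.1026 = 6.2 women.

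**3. Cost in precision.** The variance of a difference in means is proportional to 1/n₁ + 1/n₂, so a split n₁:n₂ of 60 is worth 4n₁n₂/60 balanced women. At 25:35 this is 4 × 25 × 35 / 60 = 58.3. On average, E(n₁n₂) = 60 × 59 / 4 = 885, and 4 × 885 / 60 = 59.0. The expected cost is one woman in 60.

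**4. Cost in power.** Two-sided t-test by the noncentral t distribution, standardized difference 1.30/1.61 = 0.807:

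| Analysed | Balanced | Unequal example | Average under simple randomization |
|---|---|---|---|
| All 60 | 86.8% (30/30) | 85.8% (25/35) | 86.2% |
| 50 completers | 79.9% (25/25) | 78.3% (20/30) | 79.1% |

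The average loss is 0.6 points with all 60 analysed and 0.8 points with 50 completers. With all 60 analysed, power is 80.5% at 18/42 and 79.1% at 17/43, so it falls below 80% only at 17/43 or worse, with probability 2 × P(X ≤ 17) = 0.0011, about 0.1%. The normal approximation, which matches the protocol's formula, gives 81.5% at 25/25. Its average under simple randomization, with one sixth lost in each arm, is 80.8%, a loss of 0.7 points.

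**5. Whether blocks restore 30:30.** Only if the list ends on a block boundary. Suppose blocks of 4 or 6 are drawn with equal probability and the list is cut at 60. It then stops at a block boundary in 40% of lists, after two places of a block of 4 in 20%, after two places of a block of 6 in 20%, and after four places of a block of 6 in 20%. A part-block cut at these places is balanced with probability 2/3, 3/5 and 3/5. Exact balance therefore has probability 0.40 + 0.20 × 2/3 + 0.20 × 3/5 + 0.20 × 3/5 = 0.773. A simulation of 200,000 lists gave 77.2%, with 29:31 in the other 22.8%. Six blocks of 4 and six of 6 sum to 24 + 36 = 60 and always close at 30:30, with C(12,6) = 924 possible orders of block sizes.

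**The case against.** The strongest reply is that nothing here is an error. The 30 per group stands under the sample size heading, where it can be read as a recruitment target, and a target of 30 is compatible with simple 1:1 randomization, whose expected arm size is 30. The section on assignment promises no exact balance. Unrestricted allocation is also the least predictable kind, and blocks give up some of that. All of this is fair, and it is why the point is an improvement and not a defect.

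The probabilities of 10.3% and 15.5% can also sound worse than they are. The 25 is a requirement for equal arms. When one arm has 24 the other has 36, and with one sixth lost from each arm the normal-approximation power is still 79.9%, against 81.5% at 30:30. That stands too.

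Blocks do not secure the 25 completers per arm on which the sizing depends. If ten dropouts fall at random among 60 women allocated 30:30, exactly 25/25 remain only 27% of the time. Even so, average power is then 79.7%, against 79.1% for 50 completers after simple randomization, so most of the small gain survives uneven dropout.

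Finally, the authors may have meant a shuffled list of 30 + 30 codes, which would already guarantee the split. The text does not say so, and simple randomization ordinarily means unrestricted assignment. If that was the intention, the sentence still needs correcting.

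**Conclusion.** The point holds as a minor one. The stated method delivers the stated 30 per group about one time in ten, and the expected price is one woman in 60, or 0.6 to 0.8 points of power. Validity is not affected, and power is not materially threatened. The change is still worth making because it is nearly free, makes the per-group number true, and recovers a little precision where the t-test power with 25 completers per arm is already 79.9%.

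The power figures rest on a two-sided alpha of 0.05 and on the protocol's SD and difference for CTX/BSAP, taken as stated. They say nothing about power for the primary endpoints, which the protocol defines as "the change from baseline in the frequency and severity of hot flushes as primary endpoints". The arm-size probabilities and the precision cost of one woman in 60 need only 1:1 allocation of 60; that cost applies to any comparison of means with equal variances.

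**What to change.** In Methods assignment of interventions, replace simple randomization with 1:1 permuted-block randomization with concealed, varying block sizes, from a list built to close at exactly 60. Six blocks of 4 and six blocks of 6 in random order would do. The sizes themselves are better kept in a restricted randomization record than printed in the protocol. The closing condition must be explicit, since blocks of 4 or 6 simply cut at 60 give 30:30 in only about 77% of lists.

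The guarantee requires one unstratified list and all 60 women randomized. If recruitment stops early, the arms differ by at most half a block, that is, by three women with blocks of up to six.

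The cost is one protocol line and a different generator setting, with no extra participants. The downside is slight predictability at block ends. Concealed, varying sizes and the planned blinding of researchers and participants reduce it but do not remove it.

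### Does the sentence that groups are decided after the data analysis allow data-dependent grouping?

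*Protocol*

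**What the plan says.** The section *Methods assignment of interventions* makes four statements in sequence.

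- Allocation: "Randomization will be performed using a computerized random number generator, which generated the random sequence based on simple randomization".
- Coding: "All subjects will be identified by a trial identification number and assigned a treatment code".
- Blinding: "The researchers and participants will be blinded to the treatment code until the end of the study when data will be collected and evaluated".
- Closing sentence: "The groups will be decided after the completion of the data analysis".

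Two other places describe the groups. *Methods & Analysis*, in the short description, says: "Participants will be randomized and divided into two groups to take a capsule containing probiotics and a placebo for 12 weeks". *Interventions or exposures* defines them by content: "Group 1 is the placebo group that will receive a capsule that consists of the excipient", with Group 2 receiving the *L. acidophilus* capsule.

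**The concern.** In a randomized trial nothing about group membership is left to decide once the analysis is finished. A protocol sentence that says otherwise, in the section governing allocation and blinding, deserves a second look. It can be taken in three ways:

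1. Women are sorted into groups after the results are known, which would undo the randomization.
2. The analysis groups, meaning who counts in which comparison, are settled after the results are known. With five dropouts allowed for in each group of 30 (5/30 = 16.7%), that might appear to leave room to move the estimate.
3. The sentence concerns unblinding. It then has to be squared with the sentence before it, which places the end of the blind at the end of the study, when data are collected and evaluated.

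Under the first two readings the protection of randomization and blinding would be lost. Under the third, the only question is whether the protocol names two different moments for opening the code.

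**Working it through.** **The plan's own figure.** The only computed number nearby is the sample size. The inputs, from *Sample size calculation*, are a difference of 1.30, an SD of 1.61, a type I error of 0.05 (taken as two-sided, since sidedness is not stated) and 80% power.

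n per group = 2 × [1.61 × (1.960 + 0.842) / 1.30]² = 24.08, rounded up to 25. Power at 25 per group is 81.5% by the normal approximation.

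This matches the stated 25, and 25 + 5 = 30 gives the stated final size. The disputed sentence touches none of these figures.

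**The three readings against the text.**

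| Reading of the closing sentence | Random sequence and treatment code | Groups defined by capsule, taken for 12 weeks | Blinding sentence |
|---|---|---|---|
| Membership is formed after analysis | Incompatible: the code already fixes membership | Incompatible: the capsules have been swallowed | No bearing |
| Analysis sets are chosen after analysis | Compatible, but nothing in the section mentions exclusions, dropouts or analysis sets | Compatible | No bearing |
| Identity of the groups is disclosed after analysis | Compatible | Compatible | Compatible if blinding runs through evaluation |

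Only the third reading both fits everything and has support in its surroundings, since the sentence before it is about the treatment code. That sentence alone leaves open whether the code is opened before or after evaluation. The closing sentence, read as disclosure, settles this in the stricter direction: after the analysis.

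**What each reading would do to the error rate.** This was simulated under no treatment effect, with normal outcomes, 25 women per arm and a two-sided 5% t test. It illustrates scale and describes nothing the protocol plans.

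- *Labels decoded from the code list after analysis:* 5.1% of 20,000 simulated trials were significant, and 2.5% favoured the probiotic. These are the nominal rates.
- *Labels attached to suit the result:* either direction can be called a probiotic benefit, so false claims of benefit rise from about 2.5% to about 5%.
- *Individuals regrouped to suit the result:* taking the best of 5 or of 20 arbitrary splits of 50 women gave 21% and 62% false positives (1,000 simulations each). For independent tests, 1 − 0.95⁵ = 22.6% and 1 − 0.95²⁰ = 64.2%, so the order of magnitude is right. The numbers of splits are assumptions.

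The second and third cases require ignoring the treatment code that the same paragraph assigns. The first case is what the protocol describes.

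**The dropout figure.** The 16.7% is an allowance in the sample size and says nothing about when groups are settled. Under *Variable assessment*, dietary records, body composition and fasting blood are taken only at the beginning and end. A woman who leaves early would generally have no end-of-study value for those measures that could be included or left out at will.

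**The case for a change.** The strongest case for changing the text is this. Allocation and the end of the blind are core protocol content, stated here rather than left to the SAP. The closing sentence is wrong as written, and rescuing it means replacing its main verb. Even then, the protocol words the end of the blind in two ways, which coincide only if evaluation is taken to mean the completed analysis. It describes neither an analysis under coded labels nor a database lock, so two careful teams could open the code at different times and both claim to have followed the protocol.

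Part of this stands. The verb is wrong, and the timing of unblinding is stated loosely. What does not stand is that the text permits post-hoc grouping, or that its sentences cannot be reconciled: blinding through evaluation, with disclosure afterwards, agrees with all of them.

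The obvious remedies also add little. A rule to analyse women as randomized and a record of analysis sets are commonly left to the SAP, which is not available here, and the disputed sentence does not deal with either. Releasing the code at database lock would open the blind no later, and possibly earlier, than the natural reading of the present text.

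**Conclusion.** The concern does not call for a change to the plan. The sentence contains a clerical slip, most likely for *disclosed* or *revealed*, and the surrounding text makes the harmful readings unworkable. Anyone revising the document for other reasons could tidy the verb and name one unblinding event in both sentences, but this would alter nothing the trial does or concludes.

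The effect on allocation, sample size and type I error is nil if the code is decoded as assigned. The inflated error rates above apply only to conduct that the protocol's own allocation and coding rules exclude. The conclusion assumes that the treatment codes are created and kept as the protocol describes. It also rests on a reading of intent from context, because the protocol does not itself say that the closing sentence refers to disclosure.
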